6.8.4 Adverse Events for Subjects Excluded from Safety Analysis Set

In accordance with section 3 of Chapter 3 in the 'Guidelines for Re-examination of New Drugs, etc.', the incidence status of adverse events in off-label use subjects is presented. However, those who were investigated in duplicate, those who did not receive this drug, or those who did not undergo follow-up for safety are excluded from this analysis.

For the following items, the incidence status of adverse events will be presented in a summary table. The summary table will include the number of subjects with adverse events and their incidence (%), 95% confidence interval for the incidence and the number of cases.

In addition, for the following items, the incidence status of adverse events is presented in detail. Using the latest version of MedDRA, the number of subjects with adverse events and their incidence (%) for each SOC and PT, 95% confidence interval for the incidence, and the number of cases will be included.

- Adverse events, Adverse drug reactions
- Serious adverse events, Serious adverse drug reactions
- Unexpected adverse events, Unexpected adverse drug reactions
- Unexpected serious adverse events, Unexpected serious adverse drug reactions

For the following categories, a list of events will be included:

- Serious adverse events
- Unexpected adverse events
- Unexpected serious adverse events
- Adverse events with Renal impairment
- Adverse events with Hepatic impairment

6.8.5 Other Safety Analyses

When reporting for re-examination, the following items will be categorized based on the incidence (%) by PT (Preferred Term), and information on SOC (System Organ Classes) and PT (Preferred Term) will be presented in a table.

[figure not shown]
- Serious adverse events, Serious adverse drug reactions
- Unexpected adverse events, Unexpected adverse drug reactions

[figure not shown]
At the time of reporting for re-examination, descriptive statistics of serum creatinine, glomerular filtration rate, and albumin-creatinine-ratio measured before administration of this drug and at the final visit are presented. In order to analyze whether there is a difference at the final visit compared to before administration of this drug, the paired t-test is used.

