#### 8.2.2.3 Exclusion criteria:

- Patients with previous exposure to JARDIANCE DUO®
- Hypersensitivity to active ingredients empagliflozin and/or metformin or to any of the excipients
- Moderate (stage 3b) and severe renal failure ( $\text{CrCl} < 45 \text{ ml/min}$  or  $\text{eGFR} < 45 \text{ ml/min/1.73m}^2$ )
- Acute conditions with the potential to alter renal function such as: dehydration, severe infection, cardiovascular collapse (shock), acute myocardial infarction, sepsis
- Type 1 diabetes, acute or chronic metabolic acidosis, including diabetic ketoacidosis with or without coma, history of a ketoacidosis (type 1 diabetes and diabetic ketoacidosis should be treated with insulin).
- Congestive heart failure requiring pharmacologic management, in particular those with unstable or acute congestive heart failure
- Radiologic studies involving the use of intravascular iodinated contrast materials (for example, intravenous urogram, intravenous cholangiography, angiography, and computed tomography (CT) scans with intravascular contrast materials) -  
Intravascular administration of iodinated contrast media may lead to acute renal failure and has been associated with lactic acidosis in patients receiving metformin. Therefore, in patients with  $\text{eGFR} > 60 \text{ ml/min/1.73m}^2$ , JARDIANCE DUO® must be

discontinued prior to, or at the time of the test and not be reinstated until 48 hours afterwards, and only after renal function has been re-evaluated and has not deteriorated further. In patients with moderate renal impairment (eGFR 45-60 ml/min/1.73m^2), JARDIANCE DUO® must be discontinued 48 hours before administration of iodinated contrast media and not be reinstated until at least 48 hours afterwards, and only after renal function has been re-evaluated and has not deteriorated further.

- In patients with severe infections or severe traumatic systemic disorders, JARDIANCE DUO® should be temporarily suspended, and should not be restarted until the patient's oral intake has resumed and renal function has been evaluated as normal.
- JARDIANCE DUO® should be temporarily suspended for any surgical procedure (except minor procedures not associated with restricted intake of food and fluids) before 48 hours, and not be reinstated until 48 hours afterwards, after renal function has been evaluated as normal.
- Patients with malnutrition, starvation, hypostheniam pituitary or adrenal insufficiency

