**AESI (Adverse Event of Special interest)**

The term Adverse Event of Special Interest (AESI) relates to any specific AE that has been identified at the project level as being of particular concern for prospective safety monitoring and safety assessment within this study, e.g. the potential for AEs based on knowledge from other compounds in the same class. The adverse events below reported from patients who were administered this drug in a placebo-controlled study in accordance with the approved labeling fall under any adverse events of special interest. The following are considered as AESIs:

- Vaginal moniliasis, vulvovaginitis, balanitis and other genital infection
- Increased urination
- Urinary tract infection (UTI)
- Volume depletion
- Diabetic Ketoacidosis (DKA)
- Decreased renal function:
  - Creatinine value shows a >2-fold increase from baseline and is above the ULN
- Hepatic injury defined by the following alterations of liver parameters:
  - An elevation of AST and/or ALT >3-fold ULN combined with an elevation of total bilirubin >2-fold ULN measured in the same blood draw sample.
  - An isolated elevation of AST and/or ALT >5-fold ULN (without an elevation of total bilirubin >2-fold ULN)
- Lower limb amputation
  - Amputation (i.e. resection of a limb through a bone)
  - Disarticulation (i.e. resection of a limb through a joint)
  - Auto-amputations (i.e. spontaneous separation of non-viable portion of the lower limb)

Not included in this definition are debridement (removal of callus or dead tissue), procedures on a stump (like stump revision, drainage of an abscess, wound revision etc.) and other procedures (e.g., nail resection or removal) without a concomitant resection of a limb (amputation or disarticulation).

Besides, Diabetic Ketoacidosis, which may be observed in patients treated with SGLT-2 inhibitors, also corresponds to an adverse event of special interest in this investigation, and these adverse events of special interest should be closely monitored and reported during the investigation period.

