## 14. AMENDMENTS AND UPDATES

Number	Date	Section of study protocol	Amendment or update	Reason
1	25 Apr 2018	8.2.3.2 Visit 1; Baseline Visit 8.2.3.3 Visit 2 8.2.3.4 Visit 3 10.1 Definitions of adverse events 13.Appendices	8.2.3.2 Change of data collection period 8.2.3.3, 8.2.3.4 Addition of Renal function test on Follow up visit 10.1 Addition of 'Always Serious Adverse Events' 10.1 Addition of 'AESI' case (Lower limb amputation)	- Period adjustment for completeness of data collection - Follow up for renal function - Addition of AE collection and method classification method according to BI PV process - Attached appendix separately
2	31 Jan 2019	8.2.2 Study population	8.2.2.1 Add-on therapy to 'linagliptin'	- Updates indication according to approved local label

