5.3 Summary Statistics

For continuous data, the number of subjects, mean, standard deviation, median, minimum, and maximum are presented, and for categorical data, the frequency and percentage (%) are presented.

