5.5 Other Statistical Considerations

The analysis will be conducted in consideration of the following matters, and if separate considerations are needed depending on the analysis item, the contents will be described in the relevant item of '7.1 Derivation'.

- The standard for converting Day into Month or Year is as follows: 1 month = 30.4375 days, 1 year = 365.25 days
- For all data analyses, the test statistic is a two-sided test, and the statistical significance level is based on 0.05.
- When calculating percentages from categorical demographics and baseline data, the denominator is defined as the sum of the number of subjects in each category. However, for analysis by detailed medical history/medication type, the denominator is defined as the number of subjects with medical history/medication.
- When calculating percentages of the incidence of adverse events and valid/invalid by demographics and baseline data, the denominator is defined as the number of subjects in each category. However, upon analyzing by detailed medical history/medication type, the denominator is defined as the number of subjects with medical history/medication in each category.
- When calculating the percentage of the incidence for each type of adverse event, the denominator for analyzing the safety analysis set is defined as the number of subjects in the safety analysis set. However, in the analysis of subjects excluded from safety evaluation, the denominator is defined as the number of subjects excluding those who were investigated in duplicate, those who did not receive this drug, or those who did not undergo follow-up for safety.

- In categorical data, if the cells with an expected frequency of less than 5 are more than 20% of all cells in the between group test, Fisher's exact test is used for analysis instead of the Chi-square test.
- For the confidence interval, a 95% two-sided confidence interval is calculated by applying the exact confidence interval method.
- If the total number of adverse events is 10 or less, the analysis of the incidence of adverse events by demographics and baseline data can be replaced with the list of adverse events.
- Multiple logistic regression analysis is not performed when there are two or less variables that show significant differences in the analysis of the incidence of adverse events by demographics and baseline data.

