6.8.1 Summary of Adverse Events

The number of subjects with adverse events and their incidence (%) for each SOC and PT, 95% confidence interval for the incidence, and the number of cases will be included.

- Adverse events, Adverse drug reactions^a
- Serious adverse events, Serious adverse drug reactions
- Unexpected adverse events^b, Unexpected adverse drug reactions
- Unexpected serious adverse events, Unexpected serious adverse drug reactions
- Non serious adverse drug reaction^c
- Adverse event of special interest(AESI)^d
- Adverse events leading to discontinuation^e

^aAdverse Drug Reaction (ADR): any adverse drug reaction with causality (Certain/ Probable/Likely/ Possible/ Conditional- Unclassified/ Unassessable)

^bUnexpected adverse event: the event is not included in the latest approved local label

^cNon serious adverse drug reaction: any adverse reaction which does not meet the SAE criteria

^dAdverse event of special interest(AESI) is as following 8 events:

AESI (Adverse Event of Special interest)

- Vaginal moniliasis, vulvovaginitis, balanitis and other genital infection
- Increased urination
- Urinary tract infection (UTI)
- Volume depletion
- Diabetic Ketoacidosis (DKA)
- Decreased renal function:
 - Creatinine value shows a >2-fold increase from baseline and is above the ULN
- Hepatic injury defined by the following alterations of liver parameters:
 - An elevation of AST and/or ALT >3-fold ULN combined with an elevation of total bilirubin >2-fold ULN measured in the same blood draw sample.
 - An isolated elevation of AST and/or ALT >5-fold ULN (without an elevation of total bilirubin >2-fold ULN)
- Lower limb amputation
 - Amputation (i.e. resection of a limb through a bone)
 - Disarticulation (i.e. resection of a limb through a joint)
 - Auto-amputations (i.e. spontaneous separation of non-viable portion of the lower limb)

^eAdverse events leading to discontinuation: Reason of early termination is a 'due to Adverse event' and also action taken with study drug is 'Discontinued'

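### The renal laboratory analysis compares only pre-drug with final-visit values; apart from the creatinine-doubling AESI and reported AEs, no count or shift table shows patients whose eGFR falls below 45 on treatment

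*SAP*

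**What the plan says.** Monitoring the safety profile is the primary objective (Protocol 7.1, SAP 2.1).

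- **Laboratory analysis.** SAP 6.8.5 plans that "descriptive statistics of serum creatinine, glomerular filtration rate, and albumin-creatinine-ratio measured before administration of this drug and at the final visit are presented". It continues: "In order to analyze whether there is a difference at the final visit compared to before administration of this drug, the paired t-test is used". SAP 5.3 defines the summary: "For continuous data, the number of subjects, mean, standard deviation, median, minimum, and maximum are presented". Tests are two-sided at 0.05 (SAP 5.5).
- **Event analysis.** Decreased renal function is one of eight AESIs, defined as "Creatinine value shows a >2-fold increase from baseline and is above the ULN" (Protocol 10.1, repeated in SAP 6.8.1). AEs and AESIs are reported as "The number of subjects with adverse events and their incidence (%) for each SOC and PT, 95% confidence interval for the incidence". SAP 6.8.2 also lists adverse events with renal impairment.
- **Data collected.** Protocol 8.2.3.2 to 8.2.3.4 record serum creatinine, eGFR and urine ACR at baseline and at Visits 2 and 3, where a result exists. Amendment 1 added the follow-up renal tests, and Protocol 14 gives the reason as "Follow up for renal function".
- **The value 45.** Protocol 8.2.2.3 excludes "Moderate (stage 3b) and severe renal failure", defined as CrCl or eGFR below 45. The bands 45-60 and above 60 appear in the contrast-media text.

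**The concern.** A mean change describes the group. Safety monitoring also has to show how many individuals deteriorated, and a near-zero mean can coexist with a few large falls. Conversely, a small mean shift can reach significance in several hundred pairs without anyone being harmed.

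The laboratory analysis uses two time points. For a patient who completes 24 weeks, the final visit is Visit 3, so the Visit 2 renal result is collected but not used in 6.8.5. A fall at week 12 that has recovered by week 24 would not appear there. The AESI does apply to individuals, but its threshold is far from the eGFR boundary that the protocol uses to define who may enter. At stake is whether the report can say how many treated patients moved into the renal class that the study excludes at entry.

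**Working it through.** The documents give no SD, expected change or power for renal values, and the 600 patients are a regulatory requirement. There is therefore no planned figure to reproduce. Every model input below is an assumption.

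**1. Does the AESI stand in for a count below 45?** Assume eGFR varies as creatinine to the power -k, with k between 1.0 and 1.2. The creatinine rise that takes a patient from baseline eGFR B to 45 is (B/45)^(1/k).

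| Baseline eGFR | k = 1.0 | k = 1.2 |
|---|---|---|
| 60 | 60/45 = 1.33-fold | 1.27-fold |
| 80 | 80/45 = 1.78-fold | 1.62-fold |

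Doubling coincides with 45 at B = 45 × 2^k, which is 90 for k = 1.0 and 103 for k = 1.2. Below that baseline, a patient can drop under 45 without reaching the AESI.

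**2. How many might cross, and does the t-test reflect it?** Assume baseline eGFR is normal with mean 85 and SD 18, with values below 45 removed to match the exclusion criterion, and that change is normal. Take 500 pairs. Power of the paired t-test comes from the noncentral t with noncentrality |mean change| × √500 / SD.

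| Mean change (SD) | Read below 45 | Of 500 | Crossers with doubling (k = 1) | Chance that p < 0.05 |
|---|---|---|---|---|
| 0 (8) | 1.2% | 6 | 0.4% | 5% |
| -1 (8) | 1.4% | 7 | 0.4% | 80% |
| -2 (10) | 2.3% | 11 | 3% | 99% |

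Between the first two rows the number crossing hardly changes, while the chance of a significant test goes from 5% to 80%. The test answers a different question.

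**3. Can a small group with large falls stay hidden?** Take 500 pairs with SD 8, where 15 patients (3%) lose 25 and the rest average no change. The mean change is -25 × 15/500 = -0.75. In simulation the t-test is significant in about 45% of studies.

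**4. How much of the crossing is noise?** In the zero-change row, about 92% of those who cross started below 60, and only about 19% had fallen by 30% or more. That model contains no drug effect, so a bare count below 45 needs a second measure of the size of the fall beside it.

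**5. What would a count tell the reader?** Exact 95% intervals, the method already set in SAP 5.5:

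| Patients below 45 | Tested | Exact 95% interval |
|---|---|---|
| 0 | 600 | 0 to 0.61% |
| 0 | 300 | 0 to 1.22% |
| 6 | 600 | 0.37 to 2.16% |
| 12 | 600 | 1.04 to 3.47% |

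Even an empty cell gives a usable upper bound.

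**The case against.** A reader might infer that renal safety rests solely on a mean, and that patients who fall below 45 are never counted. The documents do not support that.

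- The renal AESI is reported with subject counts and an interval.
- Every AE is tabulated by SOC and PT, and the AE definition in Protocol 10.1 includes abnormal laboratory findings. A fall the investigator considers important can therefore be counted without creatinine doubling.
- Clinically significant laboratory changes are recorded at Visits 2 and 3, although the SAP specifies no analysis of them.
- The summary includes the minimum. Under the assumptions above, the lowest of 500 final values would be below 45 in over 99% of studies, so the output would show that someone crossed, though not how many.

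A reader might also take 45 as the protocol's limit during treatment. It is stated as an exclusion at entry, and no section makes crossing it a safety endpoint.

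Two further objections stand as limits on the remedy. In a single-arm study a count of crossings cannot separate drug effect from random variation. And because renal values come from routine care, the patients tested may be a selected group.

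What survives is narrower. The event routes depend on doubling or on investigator judgement, and none applies a threshold to the recorded eGFR. The minimum gives no frequency, and a completer's Visit 2 value stays out of the laboratory analysis.

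**Conclusion.** The gap is real but limited. In the text available, renal laboratory values are analysed only as pre-drug against final visit. No count or shift table by eGFR level is planned, and the Visit 2 values that Amendment 1 added are left out of 6.8.5 for completers. The AESI would miss most falls from the 45-90 range to below 45.

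Under the assumed model the affected group is about 1.2 to 2.3% of patients (6 to 11 of 500), and about 3% of them at most would meet creatinine doubling. These figures depend on the assumed baseline distribution, the SD of change, and eGFR varying inversely with creatinine. They illustrate what could go unreported and do not predict harm, since many of these crossings would be random variation near the cut-off.

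This is an inexpensive improvement to a primary-objective analysis, and it does not invalidate the plan. One caveat: SAP 6.8.3, which 6.8 cites as part of the safety analysis, and two figures in 6.8.5 are not in the text supplied, so a relevant table could sit there.

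**What to change.** Add to SAP 6.8.5:

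1. A shift table from baseline eGFR class (above 60, 45-60) to the lowest on-treatment class over Visits 2 and 3 (above 60, 45-60, below 45).
2. The number and percentage, with exact 95% interval, of patients with (a) any on-treatment eGFR below 45 and (b) a fall of at least 30% from baseline. The 30% figure is a descriptive cut-off proposed here to help separate real falls from noise; neither document contains it.
3. A denominator of patients with a baseline and at least one follow-up value, with the number tested at each visit stated.

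Keep the mean change and paired t-test as supporting results.

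The cost is one table from data already in the eCRF. Its limits should be stated beside it: testing may be selective, and without a comparator the counts are descriptive. The table is an analysis output and implies no treatment rule.

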6.9 Effectiveness Evaluation

6.9.1 Effectiveness Assessment

For the effectiveness analysis set, descriptive statistics of glycated hemoglobin (HbA1c), [REDACTED] measured before administration of this drug and at the final visit are presented. In order to analyze whether there is a difference at the final visit compared to before administration of this drug, the paired t-test is used.

7. Derivation and Categorization for Variable

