- Concomitant medications including new medications taken since last visit : any change in the concomitant medications ( dose and dosing intervals)
- Any changes in laboratory tests if there is any lab result which was clinically significant compared to data before JARDIANCE DUO® therapy (This data is collected on the basis of medical need, i.e. independent of the NIS)
- Any adverse events noted, AESI (Adverse Event of Special interest)
- Study completion status

#### 8.2.3.4 Visit 3; 24 weeks from Visit 1

After 24 weeks from Visit 1, the patients will return for follow-up. The followings will be noted and recorded in the eCRF.

- Visit date
- Physical examination: body weight, blood pressure in sitting position (SBP, DBP)
- Any change of JARDIANCE DUO® given (Daily dose(Dosage/Administration), Start date, Date of discontinuation or continuation, Action taken, Causality)
- Effectiveness endpoints : HbA1c, [REDACTED]
- Renal Function: record Serum creatinine, eGFR, urine ACR if blood test result is available (The most recent data since last visit, except previously entered data)
- Concomitant anti-hyperglycemic agent including new medications taken since last visit : any change in the concomitant medications (dose and dosing intervals)
- Concomitant medications including new medications taken since last visit : any change in the concomitant medications (dose and dosing intervals)
- Any changes in laboratory tests if there is any lab result which was clinically significant compared to data before JARDIANCE DUO® therapy (This data is collected on the basis of medical need, i.e. independent of the NIS)
- Any adverse events noted, AESI (Adverse Event of Special interest)
- Study completion status

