### 8.3 VARIABLES

#### 8.3.1 Analysis sets

A total of 600 patients will be entered in this study, and each patient will be followed for total three times (baseline, short term 12 weeks follow up, long term 24 weeks follow up). Since T2DM is chronic disease it might be restrictive to collect safety and effectiveness data in short-term (12weeks) period, all patients will be enrolled for long-term (24weeks) surveillance.

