#### 8.3.1.4 Number of cases subject to effectiveness evaluation

These cases include those who signed the informed consent form to participate in this study as subject, visited as per the study schedule, took JARDIANCE DUO®, and were evaluated for the effectiveness.

Reflecting Ministry of Food & Drug Safety (MFDS) guideline, the cases below shall be excluded from effectiveness analysis (defined below) set in the following order:

- a. Patients excluded from safety analysis set listed in section [8.3.1.3](#)
- b. Patients with missing information of assessment of effectiveness set listed in section [8.3.2.2](#) at visit 2, visit 3

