#### 8.3.2.2 Endpoints of effectiveness

##### 8.3.2.2.1 Main endpoint

Change from baseline in HbA1c after 12 weeks and/or 24 weeks of treatment

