### 8.3.3.2 Assessment of effectiveness

#### ① HbA1c:

HbA1c should be collected within 1 month prior to baseline and after 12 weeks and 24 weeks of treatment.

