2.1 Study Objective

Primary Objective

The primary objective of this study is to monitor the safety profile of JARDIANCE DUO in Korean patient with type 2 diabetes mellitus (T2DM) in a routine clinical setting.

Secondary Objective

The secondary objective of this study is to monitor the effectiveness of JARDIANCE DUO by evaluation of the change from baseline after 12 weeks and/or 24 weeks in the glycosylated hemoglobin (HbA1c), [REDACTED]

[REDACTED] in Korean T2DM patients.

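### On the visible text, SAP 6.9.1 reports HbA1c change only at an undefined final visit, not at weeks 12 and 24, and may mix week-12 values from early leavers with week-24 values

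*SAP*

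**What the plan says.** **Endpoint.** Protocol 8.3.2.2.1 defines it as "Change from baseline in HbA1c after 12 weeks and/or 24 weeks of treatment". SAP 2.1 states the secondary objective with the same two time points.

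**Collection.** Protocol 8.3.3.2: "HbA1c should be collected within 1 month prior to baseline and after 12 weeks and 24 weeks of treatment".

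**Analysis.** Protocol 8.7.3 lists descriptive statistics of HbA1c change and names no time point. SAP 6.9.1 presents descriptive statistics of HbA1c "measured before administration of this drug and at the final visit are presented" and compares the two with a paired t-test.

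**Effectiveness set.** Protocol 8.3.1.4 takes patients who "visited as per the study schedule" and were evaluated. Its exclusion (b) reads "Patients with missing information of assessment of effectiveness set listed in section" 8.3.2.2, at visit 2, visit 3, with no conjunction between the two visits. SAP 4.2 reproduces a guideline definition that defers to the protocol. Its own study-specific sentence asks only that a patient in the safety set had an effectiveness evaluation.

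**Follow-up.** Protocol 8.3.1: "all patients will be enrolled for long-term (24weeks) surveillance". SAP 2.2 agrees. Protocol 8.2 speaks of a period of 12 or 24 weeks.

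**The concern.** The endpoint is expressed in weeks and the analysis is not. Protocol 8.7.3 leaves the time point open, so the SAP is where it should be fixed, and the readable sentence in SAP 6.9.1 does not fix it.

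Two things follow. The week-12 HbA1c values are collected from every attending patient, but no visible analysis reports them. And a patient who leaves after Visit 2 has a last HbA1c from week 12, which may or may not enter the final-visit mean depending on how the analysis set and the term are read. Such patients are expected, since SAP 6.3 tabulates early termination with reasons. Two analysts could obtain a different n and a different mean change from the same data, and the mean might belong to neither time point in the endpoint.

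**Working it through.** There is no planned figure to reproduce. The 600 patients are a regulatory requirement (Protocol 8.5, SAP 2.2), with no power, SD, effect or dropout stated. The check is a reading of the text, followed by an illustration on assumed inputs.

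**1. Is the final visit defined?** In the visible SAP the term occurs only in 6.8.5 and 6.9.1. SAP 7.1 does not derive it; the date of last visit appears there only to fill a missing drug end date. Protocol 8.1.3 and 8.2.3.6 mention a final follow-up visit without giving it a visit number.

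**2. Which patients count?** Exclusion (b) can be read two ways.

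| HbA1c available at | Excluded if either visit is missing | Excluded only if both are missing |
|---|---|---|
| Visits 2 and 3 | in; final value is week 24 | in; final value is week 24 |
| Visit 2 only | out | in; final value is week 12 if the last available value is used, none if Visit 3 is meant |
| Visit 3 only | out | in; final value is week 24 |

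The schedule clause in Protocol 8.3.1.4 leans towards the first reading, and the study-specific sentence in SAP 4.2 towards the second. The missing-data rules do not decide it. SAP 5.4 forbids replacement but does not say whether using a week-12 value as the final value is replacement; Protocol 8.7.5 says all available data are used.

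**3. Effect on n (missing rates assumed).** Let m2 and m3 be the shares missing HbA1c at Visits 2 and 3.
- Independent missingness: 600(1 − m2·m3) if both must be missing, against 600(1 − m2)(1 − m3) if either suffices.
- Everyone missing Visit 2 also misses Visit 3: 600(1 − m2) against 600(1 − m3).

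| m2 / m3 | Independent: both vs either | Nested: both vs either |
|---|---|---|
| 5% / 10% | 597 vs 513 | 570 vs 540 |
| 10% / 20% | 588 vs 432 | 540 vs 480 |
| 15% / 30% | 573 vs 357 | 510 vs 420 |

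**4. Effect on the mean.** Take the nested pattern and last available values. Let p be the share of the larger set with week-12 data only, L12 their mean change, and C12 and C24 the completers' mean changes at the two weeks. The readings differ by

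(1 − p)·C24 + p·L12 − C24 = p·(L12 − C24) = p·[(L12 − C12) + (C12 − C24)].

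The first bracketed term is selection (leavers against completers) and the second is time (week 12 against week 24). Write g for their sum. The documents give neither term. With g assumed at 0.1 to 0.3 HbA1c points and SD 1.0, and half-width = 1.96 × 1.0/√n:

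| n (both) | p | Shift p·g | 95% half-width | g at which the shift equals the half-width |
|---|---|---|---|---|
| 570 | 30/570 = 5.3% | 0.005 to 0.016 | 0.082 | 1.56 |
| 540 | 60/540 = 11.1% | 0.011 to 0.033 | 0.084 | 0.76 |
| 510 | 90/510 = 17.6% | 0.018 to 0.053 | 0.087 | 0.49 |

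At the far end, p = 30% and g = 0.3 give 0.30 × 0.3 = 0.09, slightly above the half-width of 0.080 at n = 600. Because g contains an unknown selection term, these are illustrations and not bounds.

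**The case against.** The best defence is that the schedule has one last visit, Visit 3, and all patients are planned for 24 weeks. Protocol 8.2.3.6 also sets the final follow-up visit beside premature discontinuation as alternatives, which favours reading it as the scheduled last visit. On that view the SAP reports week 24, and the and/or in the endpoint is satisfied by week 24 alone. This stands for completers, and it means a reader should not infer that SAP 6.9.1 contradicts the endpoint. It does not settle how patients without a Visit 3 value are treated.

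A reader might also infer that no week-12 analysis exists anywhere in the plan. The documents do not support that. SAP 6.9.1 is partly redacted, SAP 4.3 is announced but not shown, and 6.2, 6.6 and 6.8.3 do not appear. SAP 5.5 (valid/invalid percentages) and 7.2 (an effectiveness/ineffectiveness category) point to a further effectiveness analysis that cannot be seen. The point is confined to the visible text, where the HbA1c sentence is readable and names only the final visit.

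It is also fair to say that defining a term and adding a conjunction would alone be matters of detail. What lifts the point is that collected data for a named time point go unreported in the visible plan, and reporting them costs almost nothing.

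**Conclusion.** The point holds in limited form and is minor. On the visible text, the HbA1c result is not tied to either week in the endpoint, no week-12 change is reported, and week-12 values from early leavers may be averaged with week-24 values. The either/both question in Protocol 8.3.1.4(b) could change n noticeably under plausible missingness.

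It would be tempting to conclude that the reported mean will be materially biased. The documents do not support this: they give no dropout, SD or effect, the result depends on the share of week-12-only patients and on how leavers differ from completers, and moderate assumptions give a shift below the confidence half-width. HbA1c is a secondary objective in a single-arm study with no decision rule, so what is affected is clarity and interpretation.

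**What to change.** 1. **SAP 6.9.1:** report n, mean, SD and the paired comparison of HbA1c change separately at Visit 2 (week 12) and Visit 3 (week 24), each in patients with a baseline value and a value at that visit.
2. **Final visit:** if a final-visit result is kept, define it in SAP 7.1 as the last available post-baseline value, label it supportive, and state how this sits with the no-replacement rule in SAP 5.4.
3. **Effectiveness set:** state in Protocol 8.3.1.4(b) whether one missing visit or both excludes a patient, and align SAP 4.2, so that a patient with HbA1c at only one follow-up visit is handled the same way in both documents.

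The cost is one table from data already collected, a few lines of SAP text and a wording clarification in the protocol. The protocol presents that exclusion list as reflecting MFDS guidance, so the clarification should be checked against it.

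The final-visit wording for the renal measures in SAP 6.8.5 should be clarified separately. It uses the safety set and values recorded only where available, so the HbA1c rule does not carry over automatically.
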